Peripheral Registry of Endovascular Clinical Outcomes

"The PRIME Registry"

NCT02786173

February 19. 2016

1. Background/Introduction:

Peripheral Vascular Disease (PVD) is an epidemic alarmingly on the rise and seriously impacting many individual's quality of life. It is estimated that 20% of patients >75 years will be living with the disease by the year 2030⁽¹⁾. Critical Limb Ischemia (CLI), a serious form of PVD, is a severe blockage in the arteries of the lower extremities which markedly reduces blood-flow. CLI is a chronic condition that results in severe pain in the feet and toes and is commonly coupled with multiple co-morbidities, including, but not limited to, obesity, hypertension, diabetes, and increased age. With the increasing prevalence of PVD in an aging population, and the limitations of vascular surgery in patients with significant comorbidities, operators are gravitating more toward less invasive endovascular therapy. Endovascular therapy and vascular surgery have been proven equivalent in patients with CLI⁽²⁾.

Patients with CLI can also progress to amputation. Amputations carry a poor prognosis with significant co-morbidity and mortality⁽³⁾. Also, there continues to be a significant variation in amputation trends across the United States depending on the patient's location. This is still the case despite the current evidence linking amputations to poor outcomes ⁽⁴⁾.

In an effort to categorize the anatomical properties of peripheral vascular lesions, the Transatlantic Inter-Society Consensus (TASC) divided peripheral lesions in four categories. This classification has been recently updated to TASC II⁽⁵⁾. The TASC classification however fails to address the complexity of infra-popliteal disease in critical limb ischemia patients. Depending on the patient population, tibial vessels tend to be diffusely diseased. With the increasing complexity of CLI patients, operators are tackling these lesions more frequently and successfully.

Endovascular revascularization of patients with PVD has evolved dramatically. New technology has arisen due to a better understanding of the atherosclerotic process. Treatment modalities encompass balloon angioplasty, stenting, and atherectomy. New modalities of therapy on the horizon include bio-absorbable stents and drug eluting balloons. However, data regarding the effectiveness of these modalities in infra-popliteal disease is scarce. A need exists for reporting on real world data, to document short and long term outcomes.

Metro Health has developed a peripheral vascular intervention program with the on-going goal of being viewed as a center of excellence in the prevention of CLI. In a quest to capture procedure-related details and outcomes related to these approaches, the team at Metro Health has developed an outcomes data registry to measure and report on minimally invasive endovascular therapies, to treat advanced PVD and CLI. Multiple institutions will collectively contribute data to the registry to advance the understanding of patient management and outcomes across all endovascular treatment modalities for advanced PVD and CLI.

2. Objectives:

The primary objective of PRIME is to systematically document endovascular revascularization approaches and patient outcomes with advanced PVD and CLI both inhospital and at 1 month, 3 months, 6 months, and annually for 3 years following treatment. Secondarily, by collecting and summarizing data describing the management and outcomes of these patients, manuscripts will be generated with the goal of improving outcomes. Possible examples include:

- A decrease in the major amputation rate
- A decrease in complications associated with peripheral vascular interventions
- Improvements in the quality of life for patients with advanced PVD and CLI
- Development of mathematical tools to assess risk and outcomes
- Development of standardized testing methodologies
- Development of endovascular treatment guidelines
- Development of follow-up protocols for interventional patients with advanced PVD and CLI
- The promotion of evidence-based care models
- A reduction in the cost of treating patients with advanced PVD and CLI

3. Methods

Eligible patients with advanced PVD and CLI at medical centers participating in the PRIME Registry will be considered for enrollment in the PRIME registry. Patients will be asked to give consent within 30 days prior and 60 days post index procedure to participate. Once patients are are enrolled, their demographics, medical history, disease-relevant conditions, treatment details and outcomes will be collected for 3 years. Please refer to the initial and follow-up data form for variables collected in the PRIME registry database. Data collected meet the requirements of a "Limited Data Set" as defined by the United States HIPAA regulations. Data contain selected dates but do not include patient names, initials, or medical record numbers. Using web-based data entry this information will be placed into a secure password protected on-line database. Patients are identified in the database by a unique subject record number assigned sequentially by the electronic database and unrelated to their medical record number. This number will follow the patient for the duration of the study. These unique numbers can only be matched with patient identifiers by the individual site coordinator at each institution. It is up to the individual sites to keep a secure key linking the patient and the subject id number for accurate patient follow-up.

Oversight of the PRIME Registry is provided by a Steering Committee and Publications Committee. These committees are comprised of physicians from participating sites and the PRIME Coordinating Center. Decisions regarding protocol changes, investigator roles, addition or deletion of participating sites and publication of abstracts and manuscripts are made by these committees. Data used in abstracts and manuscripts is aggregate data only. No identifiable data is used.

Participant data will be stored in PRIME for an indefinite period of time. Participants will not be informed of the results of retrospective research studies involving the use of their information contained in PRIME.

4. Human Subjects:

Individuals to be approached for participation in PRIME will meet each of the following inclusion criteria:

- a) Adult male and female patients \geq 18 years of age.
- b) Patients who are to receive or have received lower extremity endovascular intervention
- c) Rutherford III-VI Classification
- d) Ability to provide informed consent within 30 day prior to 60 days post endovascular intervention.
- e) Ability to follow up at enrollment site.

Exclusion Criteria:

Inability or unwillingness to consent for participation in the registry.

Note: Since participation in PRIME does not involve a risk of physical harm, women of childbearing potential will not be queried as to pregnancy status or tested for pregnancy.

5. Recruitment Procedures:

Patients who meet eligibility criteria at participating PRIME centers will be invited to participate in PRIME. Unless otherwise approved, all consecutive patients will be enrolled each month. Due to the voluntary nature of this registry, sites may have limited resources. If all consecutive patients are not able to be enrolled, an alternate method of enrolling patients may be utilized, if used consistently and approved by the site's IRB and the PRIME Steering Committee. Some examples would be enrolling the first 5 or 10 eligible patients each month or enrolling only on odd numbered days. Although the recruitment process may vary by site, potential participants will be approached by a member of the research staff and will be asked to review a copy of the IRB-approved informed consent form. The research staff will review the consent form and address any questions or concerns prior to obtaining written informed consent for PRIME participation. The research staff will also address any future questions or concerns that may occur. To insure lack of selection bias, a screening log of subjects who meet eligibility criteria, but decline consent, will be kept at the site. A de-identified version of this list will be provided to the coordinating center on request.

6. Potential Risks of Research Registry Participation:

There are no risks of physical harm associated with participation in PRIME as this is an observational registry only and no treatment is added or dropped due to a patient's participation in the registry. Participation in PRIME does involve the potential risks of a breach of confidentiality of the medical record information and associated privacy of the participants. Such risks will be minimized by 1) removing direct participant identifiers (i.e., there will be no names, social security numbers, medical record numbers recorded); 2) placing recorded information on a secure server with limited access to information linking unique subject record numbers with direct participant identifiers; and 3) limiting access to the PRIME database to the appropriate IRB-approved staff at each site. Each user at a site will have his or her own log-on and password to access the database. Obtaining access to the database allows research staff the ability to enter patients' clinical data and to view their site's data. Site users are unable to access or view data from other sites.

7. Potential Benefits of Research Registry Participation:

There are no direct benefits associated with participation in PRIME. However, the use of information contained within PRIME for retrospective analyses may be of future benefit to patients with PVD. Participants in PRIME will be informed of future research studies involving PVD for which they may be eligible if they so desire.

8. Costs and Payments:

All costs associated with the implementation and maintenance of PRIME shall be supported by Metro Health through institutional support and unrestricted grants from industry. No costs will be incurred by PRIME participants. Patients will not be remunerated for their participation in PRIME. Similarly, as this is a voluntary registry, sites will not be paid to participate in the registry.

9. Addition of PRIME Registry Sites:

Once the decision is made by the PRIME Steering Committee to add a new site, the Coordinating Center will communicate with that site to insure all regulatory documents are completed. PRIME Registry members are required to have active IRB approval and a signed data use agreement to participate in PRIME. Only after these documents are received by the Coordinating Center are users at each site issued log-ons and passwords for the database. Patient consent requirements are determined by each site's IRB. IRB approval must be updated regularly based on the schedule determined by each institution's review board. Sites that have not maintained IRB approval may not continue to add patients to the registry until their IRB approval is obtained.

In order to ensure data accuracy, periodic auditing of participating sites will be conducted. The PRIME Coordinating Center will receive de-identified source documents for the first five patients enrolled at each new center; additionally, documentation for subsequent patients may be requested if deemed necessary by the reviewers. Further adjudication may be performed at random intervals.

10. Statistical Design:

Coordinating Center statisticians combine data collected from all sites in aggregate tables. Only aggregate data is used in analysis. No identifiable data are used.

Continuous data shall be expressed as means +/-standard deviations or medians (Q1-Q3) as appropriate. Discrete data shall be expressed as counts and percentages. Chi-squared, Fisher's exact tests and student's t-tests may be used as appropriate to determine statistical significance. Linear and logistic regression and survival analysis may be applied to create statistical models.

11. Protocol References:

- 1. Shammas NW. Epidemiology, classification, and modifiable risk factors of peripheral arterial disease. Vasc Health Risk Manag 2007;3(2):229-34.

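### Treated patients who die before being asked for consent are neither enrolled nor logged unless a site's IRB provides another route, so early mortality is understated to the extent that consent follows the procedure

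*Combined protocol and SAP*

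**What the plan says.** All references are to the combined protocol and SAP.

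- **Consent window (Section 3):** "Patients will be asked to give consent within 30 days prior and 60 days post index procedure to participate".
- **Eligibility (Section 4):** criterion b admits "Patients who are to receive or have received lower extremity endovascular intervention", so entry may follow treatment. Criterion d requires "Ability to provide informed consent within 30 day prior to 60 days post endovascular intervention". The exclusion is "Inability or unwillingness to consent for participation in the registry".
- **Recruitment (Section 5):** "Unless otherwise approved, all consecutive patients will be enrolled each month". Consent is written. A screening log, presented as the safeguard against selection bias, holds eligible patients who refuse. The coordinating center sees it only if it asks.
- **IRB clause (Section 9):** "Patient consent requirements are determined by each site's IRB". No waiver or surrogate route is described.
- **Outcomes (Section 2):** the primary objective covers "patient outcomes with advanced PVD and CLI both inhospital and at 1 month", with later visits up to 3 years, all timed from treatment.
- **Variables (Section 3):** "Please refer to the initial and follow-up data form for variables collected in the PRIME registry database". Those forms are not among the documents, so it is an inference that death is recorded.
- **Analysis (Section 10):** counts and percentages for discrete data, with survival analysis as an option. Nothing is said about time between procedure and consent.

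**The concern.** The clock starts at the procedure, but a patient can enter up to 60 days later, and only if alive and able to consent. This is left truncation. A patient consented after discharge cannot have died during the index stay, and one consented on days 31-60 cannot be a 30-day death. Those who died first are missing because of the outcome itself, and the log does not show them, since they never declined.

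In-hospital and 1-month outcomes belong to the primary objective. If mortality is reported there as a plain percentage of enrolled patients, a reader cannot tell whether the understatement is nil, small or large. Deaths before consent are also hard to count reliably afterwards if nobody logged them at the time.

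The concern is limited to death. Patients consented before the procedure are unaffected, and non-fatal events before consent can still be recorded for anyone who later enrols.

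**Working it through.** The plan states no mortality rate, sample size or share consented afterwards, so there is no figure of its own to reproduce. The calculation below shows direction and possible size only.

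**Inputs.** From the documents: entry up to day 60, and outcomes timed from treatment. Assumed:

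- true 30-day mortality p = 3%, with constant hazard;
- s = share of treated patients due for consent afterwards;
- consent day c uniform on 0 to C;
- u = share of survivors asked afterwards who enrol, with full uptake beforehand;
- equal risk whether consent comes before or after.

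**Formulas.** h = -ln(1 - p)/30 = -ln(0.97)/30 = 0.001015 per day, and S(t) = exp(-ht).

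- Share of later-consent patients alive when asked: A = E[S(c)] = (1 - exp(-hC))/(hC).
- Share alive when asked who then die by day 30: D = E[(S(c) - S(30)) · 1(c < 30)].
- Naive 30-day mortality = [(1 - s)p + s·u·D] / [(1 - s) + s·u·A].

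**Worked case, C = 7, s = 50%.** A = 0.99645 and D = 0.026455, so enrolled later consenters show D/A = 2.655%.

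- u = 1: (0.015 + 0.013228)/(0.5 + 0.498225) = 2.83%, relative understatement 5.7%.
- u = 0.5: (0.015 + 0.006614)/(0.5 + 0.249113) = 2.89%, relative understatement 3.8%.

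**Results at s = 50%**

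| Consent spread over days | A | D | Naive, u = 1 | Understated | Naive, u = 0.5 | Understated |
|---|---|---|---|---|---|---|
| 0-7 | 0.99645 | 0.026455 | 2.83% | 5.7% | 2.89% | 3.8% |
| 0-14 | 0.99293 | 0.022926 | 2.66% | 11.5% | 2.77% | 7.6% |
| 0-30 | 0.98492 | 0.014924 | 2.26% | 24.6% | 2.51% | 16.3% |
| 0-60 | 0.97015 | 0.007462 | 1.90% | 36.6% | 2.27% | 24.3% |

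**Sensitivity (u = 1).**

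- s = 0: no bias.
- s = 25% and 75%: 2.9% and 8.6% for days 0-7; 18.2% and 55.3% for days 0-60.
- p = 1% or 5%, days 0-60, s = 50%: 37.2% or 36.0%, so the relative size hardly depends on p.
- Half of the 30-day deaths in the first 7 days, s = 50%: 12.2% for days 0-7 and 40.0% for days 0-60.
- One-year mortality of 15% (3% by day 30), s = 50%: 1.0% for days 0-7 and 7.3% for days 0-60.

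**Does delayed entry help?** With consent timing unrelated to risk, s = 50% and u = 1, a simulation of 2,000,000 patients per C gave delayed-entry estimates of 2.998%, 2.995%, 2.984% and 2.964% for C = 7, 14, 30 and 60. The naive figures were 2.82%, 2.65%, 2.25% and 1.88%.

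Now let timing depend on risk: 20% of patients have three times the hazard, and 80% of these and 42.5% of the others are consented afterwards (0.2 × 0.80 + 0.8 × 0.425 = 50%). The true value is still 3.00%.

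| Consent spread over days | Naive | Delayed entry | Consented beforehand only |
|---|---|---|---|
| 0-7 | 2.80% | 2.95% | 2.50% |
| 0-14 | 2.60% | 2.91% | 2.50% |
| 0-30 | 2.14% | 2.80% | 2.50% |
| 0-60 | 1.71% | 2.69% | 2.50% |

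Delayed entry is closest throughout but still low. For consent within 14 days, the group consented beforehand is further from the truth than the naive rate.

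**The case against.** The strongest reply is that the defect may be nil. Death is never named as an outcome, the data forms are not to hand, and an IRB may permit another consent route. Consecutive enrolment is the default, and most patients might be consented before treatment. A delayed-entry analysis is not forbidden, and the consent date may already be held.

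Most of this stands as a limit on size, but it does not remove the mechanism. Consecutive enrolment does not require consent before treatment. The IRB clause states no alternative route. An analysis that is merely permitted is not planned.

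The size is wholly assumed, and full uptake among survivors is the high end. The days 0-60 rows are an outer limit, and nothing in the documents shows such a pattern. With s = 50%, consent within a week costs 0.1 to 0.2 percentage points at 3% mortality.

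Three objections to possible remedies also stand. The group consented beforehand cannot be presented as the unbiased figure, as the second table shows. Delayed entry needs patients at risk from day 0 and does not by itself settle composites, where an amputation before consent would precede entry to the risk set. Logging everyone not approached would come close to a procedure census at sites that sample, which are unpaid and may be short of resources.

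**Conclusion.** The point holds in conditional form and should be fixed. Following the plan as written, early mortality counted from the procedure is biased downwards wherever consent comes afterwards and the site has no other route. The amount cannot be found from the documents. Under the stated assumptions with half due for later consent, it runs from about 4-6% (relative) for consent within a week to 24-37% for consent spread over the whole 60 days, and it is zero if all consent beforehand.

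A reader might infer more, without support from the documents:

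- **That the registry's mortality figures are badly wrong.** The share and timing of later consent are unknown.
- **That losing patients who become unable to consent also lowers mortality.** They are missed too, but the sign depends on their risk relative to the others, which is not given.
- **That comparisons of sites or treatment modalities are biased as planned.** No such mortality comparison is pre-specified. If one were made later, differences in consent timing could appear as differences in outcome.

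**What to change.** Leave the consent window unchanged.

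1. **Consent timing.** Record, or use if already held, the consent date and a flag for consent before or after the procedure. A flag is needed because the date alone cannot classify same-day consent. Report by site the share consented afterwards and the days from procedure to consent.
2. **Section 10, all-cause mortality at 1 month and later.** Keep time zero at the procedure and enter later consenters into the risk set at consent, pooled so that some patients are at risk from day 0. Show the naive rate and the group consented beforehand as sensitivity analyses, and state the assumption that consent timing is unrelated to risk. Where a site or subgroup has nobody consented beforehand, report survival conditional on being alive at consent. Do not extend this to composites with non-fatal components unless the handling of events before consent is specified; keep those events in the descriptive tables.
3. **In-hospital mortality.** Report it separately for patients consented before and after the procedure, with the logged count of deaths before consent beside it. Name neither group as the unbiased figure.
4. **Section 5 log.** Extend it only to treated, otherwise eligible patients within the site's approved sampling scheme who died or lost capacity before being asked. Send de-identified counts to the coordinating center for each analysis.

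Cost: Section 10 wording, routine programming, at most two data fields, slightly more log keeping, possible site IRB agreement to the wider log, and wider intervals for early rates. Delayed entry does not recover patients who lost capacity; only the log counts them.

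### Inclusion (e), ability to follow up at the enrolling site, can be judged up to 60 days after treatment, so an early poor outcome may itself make a patient ineligible, and such patients are not logged

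*Combined protocol and SAP*

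**What the plan says.** Section 4 (Human Subjects) states that people approached for the registry "will meet each of the following inclusion criteria". Three of those criteria matter here:

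- (b) "Patients who are to receive or have received lower extremity endovascular intervention"
- (d) "Ability to provide informed consent within 30 day prior to 60 days post endovascular intervention"
- (e) "Ability to follow up at enrollment site"

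The document does not define ability, does not say when (e) is assessed, and names no other follow-up route for a patient who cannot return.

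The primary objective in section 2 covers outcomes "both inhospital and at 1 month, 3 months, 6 months, and annually for 3 years following treatment". Section 1 gives the motive: "A need exists for reporting on real world data, to document short and long term outcomes".

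On sampling, section 5 says: "Unless otherwise approved, all consecutive patients will be enrolled each month". The same section asks each site to keep a screening log as a guard against selection bias. The log covers people who are eligible but refuse consent.

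**The concern.** A criterion fixed before treatment limits the population to which the results apply. A criterion that can be settled after treatment can also depend on the result. Criterion (e) can be of the second kind, because (b) and (d) let a patient enter after the procedure and nothing ties (e) to an earlier date.

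Take a patient first approached on day 40 who had a major amputation on day 20 and now lives in a care facility. A coordinator could reasonably record that this patient cannot return to the site. A patient treated the same day with a good result would pass. The first patient is then lost even from the in-hospital outcomes, which need no return visit.

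If this happens often, the early amputation and complication rates are calculated in a cohort partly selected on those same events. Consecutive enrolment does not help, because it applies to patients who have already passed the eligibility criteria. The screening log does not help either, because a patient who fails (e) is not eligible and so never appears on it.

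**Working it through.** **Timing, from the text**

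1. All criteria must be met (section 4), so failing (e) alone excludes a patient.
2. Entry after treatment is allowed by (b), and consent up to day 60 by (d).
3. The in-hospital and 1-month outcomes (section 2) can both fall before day 60, so they can be known before eligibility is settled.
4. The log in section 5 omits patients who fail (e). The registry will therefore hold neither their number nor their outcomes.

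**Size, by illustration**

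The plan states no event rate, no share failing (e), no split between entry before and after the procedure, and no sample size. There is no figure of its own to reproduce, and every input below is an assumption.

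Let P be the true early event rate, q1 the share failing (e) among patients with an early event, and q0 the share failing among patients without one. Then

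observed rate = P(1 − q1) / [P(1 − q1) + (1 − P)(1 − q0)]

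| P | q1 | q0 | Calculation | Observed |
|---|---|---|---|---|
| 10% | 10% | 10% | 0.09 / (0.09 + 0.81) | 10.0% |
| 10% | 20% | 10% | 0.08 / (0.08 + 0.81) | 9.0% |
| 10% | 30% | 10% | 0.07 / (0.07 + 0.81) | 8.0% |
| 10% | 50% | 10% | 0.05 / (0.05 + 0.81) | 5.8% |
| 10% | 10% | 20% | 0.09 / (0.09 + 0.72) | 11.1% |

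At P = 5% the same five rows give 5.0%, 4.5%, 3.9%, 2.8% and 5.6%.

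A second illustration confines the effect to patients assessed after the procedure. Assume P = 8%, half of patients assessed afterwards, and 25% to 50% of those with an early amputation judged unable to return.

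- If no event-free patient fails (e), the excluded share is 0.08 × 0.5 × 0.25 = 0.01, or 0.08 × 0.5 × 0.50 = 0.02. The observed rate is (0.08 − 0.01)/0.99 = 7.1%, or (0.08 − 0.02)/0.98 = 6.1%.
- If 10% of event-free patients assessed afterwards also fail, 0.92 × (1 − 0.5 × 0.10) = 0.874 of the cohort is retained without an event. The observed rate is 0.07/(0.07 + 0.874) = 7.4%, or 0.06/(0.06 + 0.874) = 6.4%.
- If both groups fail equally often, the observed rate is 8%.

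The bias is favourable when q1 exceeds q0, zero when they are equal, and unfavourable when q0 exceeds q1.

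**The case against.** The strongest defence is that a registry whose objective runs to 3 years may reasonably ask that its patients can be followed, and that (e) is an ordinary feasibility rule. Its wording does not name immobile, institutionalised or distant patients. A site could read it loosely and enrol a care-home resident who can be transported. Nothing says that sites reassess ability after an event. The 60-day window comes from (b) and (d), and selection by death or by incapacity to consent would remain whatever is done about (e).

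Most of this stands. It narrows the point to the combination of (b), (d) and (e) with an unstated time of assessment. It does not remove the point, because the plan as written lets a known outcome decide eligibility and leaves no record when it does. Loose reading is only partial comfort in a multi-site registry that pools its data, since sites may read the criterion differently.

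A reader might infer that the results will certainly be too favourable, or that (e) demonstrably selects on amputation risk. The documents support neither. They give no failure shares and no outcomes for those excluded. The background remark that "there continues to be a significant variation in amputation trends across the United States depending on the patient's location" concerns variation across the country, not distance from the treating centre. The statement on poor prognosis describes what follows amputation, not whether an amputee can return.

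A reader might also conclude that (e) has to be deleted. That would exchange selection at entry for possible loss to follow-up. Telephone or records follow-up for 3 years is a real burden for sites that are unpaid (section 8) and may have limited resources (section 5).

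**Conclusion.** The concern holds in a limited form. The plan permits eligibility under (e) to be decided after in-hospital and 1-month outcomes are known, and those who fail it leave no trace in the data or the log. This goes beyond a missing definition, because outcome-dependent selection is possible even when the plan is followed exactly.

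A favourable bias in early event rates is plausible, because an amputation or a care-facility discharge can itself remove the ability to return. It is not established. The illustrations run from a substantial understatement (10% reported as 5.8%) through no bias to a modest overstatement (11.1%). They rest wholly on assumed failure shares, and the plan collects nothing from which those shares could be estimated.

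**What to change.** 1. State in section 4 that (e) is judged only on circumstances before the index procedure, such as residence, and never on events after it. This also applies to patients first approached after treatment.
2. Extend the section 5 screening log to patients who fail (e), with the reason, so that their number can be reported and compared across sites.
3. Where consent is given, keep patients who later cannot return in the in-hospital outcomes, and treat their later visits as missing.

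The cost is a short protocol change and a slightly longer log. Sites must reconstruct pre-procedure circumstances for patients approached late, and somewhat more data will be missing at later visits. Removing (e) altogether and following patients by telephone or records is an option for the Steering Committee to weigh against site resources. It is not needed to close the outcome-dependent route through (e).

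### The screening log meant to guard against selection bias lists only decliners, so treated patients who die or lose capacity before being asked, and any missed in error, leave no trace

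*Combined protocol and SAP*

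**What the plan says.** Section 5 (Recruitment Procedures) describes one log, its purpose and its content: "To insure lack of selection bias, a screening log of subjects who meet eligibility criteria, but decline consent, will be kept at the site". The coordinating center sees it only if it asks: "A de-identified version of this list will be provided to the coordinating center on request".

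The same section invites all patients who meet the eligibility criteria and sets the default: "Unless otherwise approved, all consecutive patients will be enrolled each month". A site with limited resources may use another rule if it is applied consistently and approved by its IRB and the Steering Committee: "Some examples would be enrolling the first 5 or 10 eligible patients each month or enrolling only on odd numbered days".

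Section 3 (Methods) gives the consent window: "Patients will be asked to give consent within 30 days prior and 60 days post index procedure to participate". Section 4 (Human Subjects) admits patients already treated. It makes ability to consent in that window inclusion criterion (d), and its only exclusion is being unable or unwilling to consent. Section 9 leaves consent requirements to each site's IRB.

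The primary objective in Section 2 covers "patient outcomes with advanced PVD and CLI both inhospital and at 1 month, 3 months, 6 months, and annually for 3 years following treatment".

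**The concern.** The log's purpose is wider than its content. Selection into a consent-based registry can happen in several ways: refusal, death or incapacity before the request, failure to approach, and sampling by rule. The log captures refusal only.

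Death and incapacity matter most because they are linked to outcome. Where consent follows the procedure, a patient must survive, and remain able to consent, to be counted. In-hospital and 1-month results are then conditional on reaching consent, which pushes early mortality downward. Failure to approach matters because, without a count of those who should have been asked, nobody can check whether consecutive enrolment happened.

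The registry intends to produce risk tools, treatment guidelines and real-world outcome data, so early event rates are among its main products.

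**Working it through.** **Who is visible.** The documents state no sample size, event rate or enrolment figure, so there is no plan figure to reproduce. The first check is to place each kind of treated patient meeting (a) to (c), that is adult, treated and Rutherford III to VI, against the two records.

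| Disposition | In registry | In log |
|---|---|---|
| Consented | yes | no |
| Asked and declined | no | yes |
| Died or lost capacity before being asked | no | no |
| Missed contrary to the invitation and consecutive rules | no | no |
| Left out under an approved alternate rule | no | no |

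No other section fills the empty rows. The audits in Section 9 are for data accuracy, and the detail given concerns enrolled patients. Section 3 says "Data contain selected dates but do not include patient names, initials, or medical record numbers", so an enrolment against an odd-day rule or above a monthly cap might be detected from dates, but an omission cannot. Section 10 mentions survival analysis as an option and says nothing about entry at consent.

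**How large the effect could be.** All inputs here are assumptions.

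- m = true 30-day mortality, 3% (30 deaths per 1,000 treated).
- Constant hazard: h = -ln(1 - 0.03)/30 = 0.001015 per day.
- s = share of patients consenting after the procedure; the rest consent before it and lose no deaths.
- c = day of consent for those consenting afterwards.

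Unrecorded deaths per 1,000: u = s × 1000 × E[1 - exp(-h × min(c, 30))].

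With c uniform over days 0 to 7, 7h = 0.00711 and the expectation is 1 - (1 - exp(-7h))/(7h) = 0.00355. All losses fall before day 30, so observed mortality = (30 - u)/(1000 - u).

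| s | u (of 30) | Observed 30-day mortality |
|---|---|---|
| 0% | 0 | 3.00% |
| 25% | 0.9 | 29.11/999.11 = 2.91% |
| 50% | 1.8 | 28.23/998.23 = 2.83% |
| 100% | 3.5 | 26.45/996.45 = 2.65% |

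Changing one assumption at a time, with s = 100%:

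- **Mortality.** At m = 1%, u is 1.17 of 10; at m = 5%, 5.96 of 50 (days 0 to 7).
- **Timing of deaths.** If half of the 30-day deaths fall in the first 7 days, u rises from 3.5 to 7.5 of 30.
- **Timing of consent.** Uniform over days 0 to 30 gives u = 15.1 of 30. Uniform over days 0 to 60 gives 0.5 × 15.08 + 0.5 × 30 = 22.5 of 30. The share alive at consent is then (1 - exp(-60h))/(60h) = 0.970, so the enrolled-only rate is (30 - 22.54)/970 = 0.77%. This is an extreme use of the window.

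**What a delayed-entry analysis recovers.** In a simulation of 2,000,000 patients with consent uniform over days 0 to 60 and a true value of 3%, left-truncated Kaplan-Meier gives 3.00% when entry time is independent of risk. If 20% of patients have five times the hazard and all consent on days 30 to 60, it gives only 1.66%. It corrects part of the problem, under an assumption the registry data alone cannot confirm.

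**The case against.** Much of the case on the other side stands.

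- A reader might infer that the log drops eligible patients. Under the protocol's definitions, a patient who dies or loses capacity before being asked arguably fails criterion (d) and meets the exclusion, so is not eligible at all. The accurate description is a treated patient meeting (a) to (c). That leaves the gap open: the definitions themselves remove these patients from view.
- A reader might infer that no site has a usable denominator. At a site that fully follows the invitation and consecutive rules, enrolled plus decliners does cover the protocol-eligible patients. What is missing there is any means of showing that the rules were followed, and the wider (a) to (c) denominator.
- A reader might count patients skipped under an approved rule as a failure of the log. The documents do not support that: such rules need approval and consistent use, and odd-day sampling is not necessarily biased. It is a matter of generalisability.
- Consent may be given up to 30 days before the procedure, and a site's IRB may set a different requirement. Some sites may lose nobody.
- Left-truncated Kaplan-Meier does not directly estimate in-hospital mortality, because discharge ends that risk and patients consenting later contribute no in-hospital time.

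None of this lets a list of decliners show who was lost before being asked.

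**Conclusion.** The concern holds as a mismatch between the log's purpose and its scope. That part rests on the text and is firm. The bias itself is possible rather than shown. A reader might infer that early mortality in this registry is understated; the documents do not support that, since they give neither mortality nor consent timing, and the effect is zero if all consent precedes the procedure.

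Under the illustrative assumptions, early consent costs little: 3.00% is seen as 2.91% to 2.65% when post-procedure consent falls within a week. Only late consent for everyone gives a severe distortion, to about 0.8%. The present log could not tell these situations apart. This should be changed, though the registry can proceed meanwhile.

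**What to change.** In Section 5, say that the log serves to assess selection bias rather than to guarantee its absence. Have each site keep aggregate counts of treated patients meeting (a) to (c), split into:

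- enrolled;
- declined;
- died or became unable to consent before being asked;
- missed or not approached;
- not sampled under the approved rule;
- unable to follow up at the site.

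Send the counts on a fixed schedule instead of on request, and report the enrolment flow with the main results. Reconcile the log's wording with Section 4: unwillingness to consent is an exclusion, so read literally a decliner cannot also meet the eligibility criteria.

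If procedure and consent dates are collected (the data form is not supplied here), report early outcomes separately for patients consented before and after the procedure. Add 30-day mortality with delayed entry at consent as a sensitivity analysis, stating that it assumes entry time is independent of risk. Do not use delayed-entry Kaplan-Meier for in-hospital mortality.

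The cost is a short amendment and modest clerical time, which is a real request given that "sites will not be paid to participate in the registry". Classifying non-participants needs some chart review on site, but sending counts only keeps patient-level data on non-consenters out of the registry. The sensitivity analysis will be imprecise if few patients consent before or soon after the procedure. The counts reveal the selection; they do not remove it or supply the missing outcomes.
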